**Al Azhar Faculty of Medicine
Urology department**

**Anatomical and Functional Outcome of Penile Skin Graft
versus Buccal Mucosal Graft for Urethral Substitution in Long
segment Anterior Urethral Strictures: A Prospective
randomized Study**

**A thesis proposal submitted for partial fulfillment of MD degree
in Urology**

BY

[name]

Assistant Lecturer of Urology, Faculty of medicine, Al Azhar University

Under the supervision of

[name]. [name]

Emeritus Professor of Urology, Faculty of medicine, Al Azhar University

[name]. [name]

Professor of Urology, Faculty of medicine, Al Azhar University

[name] [name]

Lecturer of urology, Faculty of medicine, Al Azhar University

Date: 30/06/2022

Introduction

Urethral stricture disease is a common problem faced by urologists worldwide.

The treatment of urethral strictures varies from urethral dilation to urethroplasty. It depends significantly on urethral stricture length and location, degree of spongiofibrosis, and underlying etiology.

Urethroplasty is classified into excision with primary anastomosis or augmentation urethroplasty. The direct anastomosis technique is suitable for short segment stricture (≤ 2 cm), while lengthy stricture requires substitution.[1]

Grafts or local skin flaps can be used to substitute the urethra. Although local skin flaps might yield equivalent results to those of grafts, flaps are associated with more complications like penile torsion, shrinkage and tissue necrosis. Moreover, harvesting a flap is technically more challenging. Therefore, grafts are preferred in substitution urethral reconstruction (UR) whenever possible.[2]

Numerous grafts have been described in UR: genital and extragenital skin, tunica vaginalis, bladder mucosa, colonic mucosa, buccal mucosa, lingual mucosa, and tissue-engineered grafts.

Currently, penile skin graft (PSG) and buccal mucosal graft (BMG) are the most widely used materials for substitution.[3]

BMG is the current gold standard for substitution urethroplasty, as it is a readily available, strong neurovascular tissue that resists infection. However, BMG harvest may be associated with donor site scarring, perioral sensory defect, and jaw opening impairment. Also, BMG harvest is contraindicated in patients with oral morbidity (e.g., oral leucoplakia, poor oral hygiene, heavy tobacco

smoking/chewing, previous irradiation, or previous BMG), and in those at high risk for general anesthesia.[4, 5] The possible advantages of PSG over BMG include: same operative field, shorter operation time, more familiar place for urologists, can be done with regional anesthesia, and can be used when longer grafts are needed.[6]

The substitution urethroplasty approach can be ventral, dorsal, lateral, or dorsolateral. Barbagli and Kulkarni have proposed unilateral mobilization of the urethra to one side with sparing of central tendon of perineum and dorsolateral placement of the BMG in order to preserve the blood supply to the urethra and maintain the neuro-vascular integrity of the bulbospongiosus muscle.[7, 8] Moreover, through the perineal wound the pendulous urethra is accessed by penile eversion through the wound and no incision is made on the penis except for meatotomy, this minimizes chances of wound infection and fistula formation.[9, 10]

Several studies were conducted to compare functional and anatomic outcomes after substitution urethroplasty with PSG and BMG for anterior urethral stricture disease. Most studies reported superior outcomes with BMG over PSG.

However, most previous studies were:

- ▶ Retrospective and very few were prospective randomized studies
- ▶ Some studies were done on lichen sclerosis cases that have an adverse effect on the PSG outcome.
- ▶ The follow-up duration was longer for PSG patients.
- ▶ Stricture length was usually longer for PSG cases.[11]

Study problem and hypothesis:

This study aims to compare the PSG and BMG for substitution of long anterior urethral strictures using one-sided dorsal perineal approach.

- We hypothesize that:

- ① Conducting a well-designed prospective, randomized study can help identify which technique is better than the other.
- ② Using the one-side dorsal approach can improve the outcomes of both techniques and identify their advantages and disadvantages.

Patients and Methods:

Study type: a prospective randomized interventional study.

Sampling: hospital-based sample.

Allocation: Patients will be randomly allocated into one of 2 groups.

Intervention Model: The 1st group: PSG cases, the 2nd group: BMG cases. Patients in the PSG group will be compared with BMG group patients.

Randomization: Block randomization will be utilized, with a block size of 2.

Estimated Enrollment: 60 participants (30 cases in each group).

Masking: Open-label

Study Location: Al-Hussein and Sayed Galal, Al-Azhar University Hospitals, Cairo, Egypt.

Study Population

Inclusion criteria

- The study will include patients with long segment anterior urethral stricture (>2 cm).

Exclusion criteria

- Urethro-cutaneous fistula, urethral abscess or diverticulum.
- A scarred and unsalvageable urethral plate or scarred perineum.
- Lichen sclerosis (Balanitis xerotica obliterans).
- Unhealthy/unavailable buccal mucosa.

Pretreatment evaluation:

- ✚ Medical and surgical history including age, cause of stricture, presence of medical diseases like diabetes mellitus, and history of previous urethral procedures.
- ✚ The following questionnaires will be used for assessment of LUTS, sexual function and satisfaction, and oral health:
 - IPSS (international prostate symptom score).[12]
 - IIEF-5 Score (international index of erectile function).[13]
 - MSHQEJD (male sexual health and ejaculatory dysfunction questionnaire).[14]
 - BMG questionnaire for brief oral health status examination (BOHSE).[15]
- ✚ Physical examination including BMI, oral, abdominal and penile examination and presence of supra-pubic catheter.
- ✚ Laboratory investigations (urine analysis, urine culture and sensitivity, complete blood count, bleeding profile and serum creatinine levels).
- ✚ Uroflowmetry (UFM) if feasible.
- ✚ Radiologic investigations:
 - # Retrograde urethrography (RGU) and micturating cystourethrography (MCU).
 - # Renal and bladder ultrasound with estimation of pre and post voiding residual urine.

An informed consent will be signed by each patient.

surgical technique:

The patient will be put in lithotomy position then a midline perineal incision will be made and a distal penile skin or buccal mucosal graft will be harvested.

Buccal graft harvest Using a marking pen, the graft will be outlined 2.5 cm wide and as long as is required. Bupivacaine 0.5% with epinephrine will be injected underneath the graft for good analgesia and intraoperative hemostasis. The graft

will be then incised and dissected off of the buccinator muscle, while avoiding Stensen's duct. The defect will be left open to close by secondary intention, as it is less painful. The graft will be pinned out and defatted/thinned on the back table. It will be kept in saline until the time of implantation. [16]

Penile skin graft harvesting: PSG will be obtained by a circumferential distal penile incision and harvesting the graft from the lateral distal penile shaft in a transverse or longitudinal direction subcoronally. The subepithelial tissue of graft will be thinned to the level of the dermis and tailored as necessary.[17]

The pendulous urethra will be accessed by penile eversion through the perineal wound. The urethra will not be separated from the corporal bodies on one side and will only be mobilized from the midline on the ventral aspect to beyond the midline on the dorsal aspect (Figure 1A). The anterior urethra will be opened on the dorsolateral aspect (Figure 1B). The free graft will be sutured to the opened urethral edge and graft will be quilted on the ventral tunica of the corporal bodies (Figure 1C). Thereafter, the free edges of graft and opened urethra will be closed over a 14 Fr silicone catheter (Figure 1D). A surgical drain will be put if needed. [18, 19]

[figure not shown]

Figure 1: (A) Mobilization of urethra beyond midline dorsally, (B) Dorsal urethrotomy, (C) Graft sutured to medial urethral margin, (D) Free margin of the graft sutured to lateral urethral margin.[19]

The complications will be graded using the modified Clavien-Dindo classification system.[20]

FOLLOW UP: The follow up period will be at least 6 months

The patients will be treated with broad spectrum IV antibiotics for 48–72 h, which will be followed by oral antibiotics until catheter removal. The patients will be also treated with analgesics, bladder antispasmodics, stool softener, and diazepam to help prevent erections.

The patients will be discharged after the drain is removed, if it was put, usually within 2–3 days after surgery.

They will be followed up at the clinic after 1 week for wound assessment. Another visit will be scheduled 30 days after surgery where the urethral catheter will be removed and a voiding urethrogram will be taken.

A 3 monthly follow-up visits thereafter will be scheduled for assessment of LUTS with performing simple uroflowmetry, treatment satisfaction and sexual function.

The follow-up will rely mainly on patient symptoms (subjective diminished force-of-stream, UTI, urinary retention, etc.), while diagnostic procedures such as urethroscopy and/or retrograde urethrogram will be done selectively.

OUTCOME

Anatomic (Objective): Urethral patency will be evaluated by

- ✓ Uroflowmetry, and
- ✓ Urethrography.

Functional (Subjective): LUTS, sexual function, and satisfaction. Through:

- ✓ IPSS (international prostate symptom score).[12]
- ✓ IIEF-5 Score (international index of erectile function).[13]
- ✓ MSHQEJD (male sexual health and ejaculatory dysfunction questionnaire).[14]
- ✓ USS-PROM (patient reported outcome for urethral stricture surgery).[21]

References

- [3] **Levy ME and Elliott SP. (2017).** Graft use in bulbar urethroplasty. *Urol Clin North Am* 2017; 44:39-47.
- [4] **Ahmed ABS et al (2021).** Substitution Urethroplasty in the Management of Anterior Urethral Stricture Disease - a Study of 50 Cases. *Saudi J Med.* 2020; 6(6): 169-175.

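### A fixed, published block size of 2 in an open-label trial lets a recruiter know up to half of the allocations in advance

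*Protocol*

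**What the plan says.** Under Patients and Methods the Protocol sets two groups of 30 and states "Randomization: Block randomization will be utilized, with a block size of 2". The block size is a single fixed number, printed in the protocol. The same list gives "Masking: Open-label".

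The trial runs at two hospitals: "Study Location: Al-Hussein and Sayed Galal, Al-Azhar University Hospitals, Cairo, Egypt". The Protocol does not say who enrols patients or whether the hospitals share one list.

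Three other statements bear on the point. The Introduction lists among the possible advantages of PSG that it "can be used when longer grafts are needed". It then criticises earlier studies because "Stricture length was usually longer for PSG cases". The inclusion criterion admits any anterior stricture longer than 2 cm, with no upper limit.

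**The concern.** A 1:1 block of 2 can only be PSG-BMG or BMG-PSG. Once the first graft of a pair is known, so is the second. In an open-label comparison of two visibly different donor sites, the surgical team sees which graft the last patient received. Sealed envelopes would not help: they hide the card, but the next allocation follows from the previous one and the published block size.

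A recruiter who knows the next graft can defer a patient, change the order of two patients, or apply a judgement-based exclusion (unsalvageable urethral plate, unhealthy buccal mucosa) more or less strictly. The Introduction supplies a possible reason to do so, since it links PSG to longer grafts. Steering of that kind could recreate the stricture-length imbalance that the Protocol faults in earlier work.

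The first hypothesis rests on a well-designed randomised comparison. If steering occurred, an arm difference would mix the effect of the graft with the selection of cases. Baseline urethrography, cause of stricture and previous procedures could reveal part of it. Degree of spongiofibrosis is not named in the pretreatment evaluation, so selection on it might go unseen.

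**Working it through.** **Inputs from the Protocol:** 2 arms, 30 per arm, 60 in total, block size 2, open-label, two hospitals. There are 60/2 = 30 blocks, each with one patient per arm, which agrees with the stated 30 per group. The Protocol gives no figure for predictability.

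**Predictability when the whole list is seen (exact enumeration).** An allocation is certain when one arm has no places left in the block. The best guess names the arm with more places left, and a tie counts one half.

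| Design | Certain | Correct guesses |
|---|---|---|
| Block of 2 | 1/2 (30 of 60) | 3/4 (45 of 60) |
| Block of 4, size known | 1/3 (20 of 60) | 17/24 = 70.8% |
| Block of 6, size known | 1/4 (15 of 60) | 41/60 = 68.3% |
| Blocks of 4 and 6 mixed, both sizes known (simulated) | about 5.6% | about 69.1% |

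**One list shared by two equal hospitals, no exchange, block of 2.** A recruiter knows an allocation only if it is second in its pair (1/2) and the first was at the same hospital (1/2): 1/2 × 1/2 = 25%, provided the list number is visible. Correct guesses are 0.25 + 0.75 × 0.5 = 62.5%. If the number is hidden, nothing is certain, but naming the opposite of the last graft seen is still right 62.5% of the time.

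**Illustration of bias.** The shift d is an assumption; the Protocol gives no such figure. So is the analysis: a two-sample t-test on a continuous outcome with SD 1. Suppose each patient whose allocation is guessed is chosen to be d SD better if one graft is expected and d SD worse if the other is. With p the share of correct guesses, the expected difference between arms is 2d(2p − 1):

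- block of 2, whole list: 2d(2 × 0.75 − 1) = d
- block of 2, shared list: 2d(2 × 0.625 − 1) = 0.50d
- mixed 4 and 6, whole list: 2d(2 × 0.69 − 1) = 0.76d
- mixed 4 and 6, steering on certain allocations only: 2d × 0.056 = 0.11d

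For the block of 2 with the whole list seen, the SD within an arm is √(1 + d²/4) and the noncentrality is d / [√(1 + d²/4) × √(2/30)], with 58 degrees of freedom. At d = 0.5 this is 0.5 / (1.031 × 0.258) = 1.88. The other two rows are simulated.

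| Two-sided type I error (nominal 5%) | d = 0.1 | d = 0.25 | d = 0.5 |
|---|---|---|---|
| Block of 2, whole list seen | 6.7% | 15.7% | 45.5% |
| Block of 2, shared list | about 5.5% | about 7.5% | about 15% |
| Mixed 4 and 6, steering on best guesses | 5.9% | 10.9% | 27.8% |

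**Cost in balance.** Sums of 4s and 6s are even, so on one list of 60 the last block can leave at most two more in one arm: 31/29, with efficiency 4 × 31 × 29 / 3600 = 0.999. With one list per hospital the worst case is 33/27, with efficiency 4 × 33 × 27 / 3600 = 0.990.

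**The case against.** The predictability arithmetic is not in dispute. The objections concern motive, size and the value of the remedy.

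- **Motive.** The remark on longer grafts is one item in an introductory list of possible advantages, not a trial rule. The methods let the buccal graft be as long as needed, and the Introduction calls BMG the gold standard, so the direction of any preference is unclear. This stands: the text supports that steering could happen, not that it would, nor in which direction.
- **Route.** A criterion with no upper limit leaves no discretion in itself, because a long stricture qualifies whichever arm is next. This also stands. The routes are deferral, reordering and the judgement-based exclusions.
- **Spongiofibrosis.** The Introduction names it as a determinant of the type of stricture treatment, not of the choice of graft, and unsalvageable plates are excluded. It is a side point, and the concern does not depend on it.
- **Type I error.** The figures rest on an assumed shift, an assumed test and, at 45%, one observer who sees the whole list and acts on every predictable allocation. They illustrate; they do not estimate.
- **The remedy.** Larger mixed blocks lower correct guesses only from 75% to about 69%, and 76% of the bias remains if a recruiter acts on every best guess. That is true. The gain is in certainty, from 50% to about 6%. A hunch about which arm is behind is a weaker basis for deferring a patient than knowing the next graft.

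**Conclusion.** The concern holds and should be fixed. No permuted block is more predictable than a block of 2, and this one is fixed, published and used in an open-label trial. Up to 30 of 60 allocations are certain in advance and 75% can be guessed by someone who has seen the whole list. With one list shared by two equal hospitals that exchange nothing, the figures are 25% at most and 62.5%.

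Confidence is high for predictability, which needs only the stated design and sight of earlier allocations. Whether bias would follow, and how large it would be, cannot be read from the Protocol. This is a rule the Protocol states, not a detail left to an analysis plan, and no later analysis can make allocations unpredictable after patients have been enrolled.

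**What to change.** In the Randomization line, replace the block size of 2 with computer-generated permuted blocks of randomly varying size. Use larger sizes (for example 4 and 6), keep them out of the protocol and from those who recruit, and reveal each allocation only after eligibility and consent are recorded. Keep 1:1 and 60 patients.

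Withholding the sizes is part of the fix, because it removes the roughly 6% of allocations that stay certain when they are known. It does not abolish guessing: a recruiter who tallies a whole list and names the arm that is behind is still right about 69% of the time. One list across both hospitals is preferable to one per hospital, since separate lists show each site its full sequence. With a shared mixed list and only the own site seen, correct guesses fall to about 58% and the bias to about 0.32d.

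The cost is one phrase and a new list. Arm sizes may differ slightly: at worst 31/29 on one list (0.1% loss of efficiency), or 33/27 with a list per hospital (1%).

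### Randomisation uses fixed blocks of 2 and names no stratification factor, leaving stricture length to chance; stratifying on length with longer, concealed blocks would be a cheap improvement

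*Protocol*

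**What the plan says.** Under Patients and Methods, the allocation rests on two sentences: "Patients will be randomly allocated into one of 2 groups" and "Block randomization will be utilized, with a block size of 2". Planned enrolment is 60, 30 per group, and masking is given as "Masking: Open-label". No stratification factor is named there or elsewhere in the protocol, and the number of randomisation lists is not given. Two hospitals of one university take part.

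Stricture length appears in three other places:

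- The Introduction says of the treatment of urethral strictures in general: "It depends significantly on urethral stricture length and location, degree of spongiofibrosis, and underlying etiology".
- The Introduction's list of limits of earlier PSG v BMG studies includes "Stricture length was usually longer for PSG cases". The same list says that most of those studies were retrospective.
- The inclusion criterion is an anterior stricture longer than 2 cm, with no upper limit.

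The pretreatment evaluation includes retrograde urethrography and micturating cystourethrography for every patient.

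**The concern.** The protocol singles out length as something that made earlier comparisons hard to read, and then leaves length in this trial to chance. Patients may have strictures of just over 2 cm or much longer ones. Blocks of 2 in order of arrival keep the arm sizes equal but do nothing to balance length.

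If the arms happen to differ in length, the unadjusted comparison is shifted to the extent that length affects outcome, and readers will ask whether graft or length explains the result. Stratification belongs to the allocation list. It must be in place before the first patient and cannot be added by an analysis plan.

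The block size adds a second weakness. In an open-label trial, whoever knows that blocks hold two patients also knows, once the first is allocated, where the second will go. The Introduction gives a reason why length might then influence enrolment: it names the need for longer grafts as a setting in which PSG can be used.

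**Working it through.** **Inputs.** From the protocol: 60 patients, 30 per arm, blocks of 2, open-label, strictures above 2 cm. Not in the protocol, hence assumed: length is expressed in SD units and its mean difference is treated as approximately normal; the share of long strictures is 30% to 50%.

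**The plan's own figure.** 60 / 2 = 30 blocks, each giving one patient to each arm, so one completed list yields exactly 30 v 30. This agrees with the stated enrolment.

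**Chance imbalance in mean length.** Under randomisation the standardised difference between arms has mean 0 and standard error sqrt(2/30) = 0.258. The two-sided probability of a difference beyond d is 2 × [1 − Φ(d/0.258)].

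| Difference in mean length | Either direction | PSG longer |
|---|---|---|
| 0.3 SD | 24% | 12% |
| 0.5 SD | 5.3% | 2.6% |
| 0.8 SD | 0.2% | 0.1% |

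**Chance imbalance in the share of long strictures.** A gap of 20 points is 6 patients in 30. Simulation of 30 unstratified blocks of 2 (200,000 runs) gives:

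| Gap between arms | 30% long | 50% long |
|---|---|---|
| 10 points or more | 48% | 52% |
| 20 points or more | 12% | 15% |
| 20 points or more, PSG longer | 6% | 8% |
| 30 points or more | 1.6% | 2.7% |

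**What such a gap could do.** The protocol does not give the effect of length on outcome, so this step is illustration only. The shift equals the imbalance times the difference in success between short and long strictures.

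- Success differing by 10, 20 or 30 points (assumed): a 20-point imbalance shifts the comparison by 2, 4 or 6 points.
- Success of 90% in short and 65% in long strictures (assumed): 0.20 × (0.90 − 0.65) = 0.05, or 5 points.
- For scale, with success near 78% in both arms, the standard error of the difference is sqrt(2 × 0.78 × 0.22 / 30) = 0.107, or 10.7 points. The 5-point shift is about half a standard error.

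**Predictability.** On one list with blocks of 2, the second patient of each block is determined: 30 of 60 allocations. Someone who guesses the first of each pair at random and knows the second is right 0.5 × 0.5 + 0.5 × 1 = 75% of the time.

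**After the fix.** With two length strata and blocks of 4 and 6, an unfinished block leaves at most 3 more patients in one arm within a stratum. The number of long strictures can therefore differ by at most 3. The gap in share is largest when the short stratum is off by 3 the other way: the arms are then 30 v 30 and the gap is 3/30 = 10 points. If both strata are off in the same direction, the arms differ by 3 + 3 = 6 patients, that is 33 v 27. These are worst cases.

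**The case against.** The strongest reply is that nothing here is wrong. Unstratified randomisation is valid, and the test's error rate already covers chance imbalance. Adjustment for length may stand in an analysis plan that was not available for this review. Even on unfavourable assumptions the shift is about half a standard error, in a minority of trials. All of this stands, and it is why the point is an improvement and not a defect.

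Several stronger readings are tempting, but the documents do not support them:

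- *One list runs across both hospitals.* The protocol is silent on the number of lists. Nor does it suggest that hospital affects outcome.
- *The imbalance of earlier studies will recur.* That imbalance was systematic and ran towards longer strictures with PSG, in mostly retrospective studies. Randomisation removes it. What remains is chance, equally likely either way, and a difference of 0.5 SD or more towards PSG has a probability of only 2.6%.
- *Length is a proven strong prognostic factor.* The Introduction's sentence on length concerns the choice among treatments, from dilation to urethroplasty. That length matters to outcome can be inferred from its place in the list of earlier weaknesses, but no effect size is given.
- *Stratification would be worth 6 to 20 extra patients.* That figure is 60/(1 − r²) = 66 to 80 for an assumed correlation r of 0.3 to 0.5. It is the gain from covariate adjustment, which does not need stratified allocation.
- *Four strata of hospital by length are needed.* With hospitals split 70:30 and 30% long strictures (assumed), the smallest stratum has 60 × 0.3 × 0.3 = 5.4 patients, which is thin.

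The reply does not cover two things. Balance by design cannot be added later, and blocks of 2 remain predictable whatever the analysis does.

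**Conclusion.** The point holds as a recommended, low-cost design change. The allocation method is fixed in the protocol without stratification, and length is the factor that the protocol itself names as unequal in earlier comparisons. The 24% follows from 30 per arm and a normal approximation; the 12-15% also needs the assumption that 30-50% of strictures are long. The effect on the graft comparison cannot be sized from the protocol; the 2 to 6 points shown rest wholly on assumed success rates.

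Predictability does not depend on those assumptions: with blocks of 2, every second allocation is known to anyone aware of the block size, which the protocol states. Whether it would be exploited cannot be judged from the document. Stratifying while keeping blocks of 2 would leave this weakness in place.

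**What to change.** Replace the randomisation sentence with one that states:

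- randomisation stratified on stricture length alone, at two levels read from the pre-operative urethrogram, with the cut-point fixed before the first patient;
- concealed permuted blocks longer than 2, for example varying between 4 and 6;
- the length stratum accounted for in the PSG v BMG comparison.

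Stratifying by hospital as well is optional.

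The cost is two lists instead of one and a short change of text. No extra patients or tests are needed, because urethrography is already in the pretreatment evaluation; length must be recorded before the patient is allocated. The downside is that the arms may end a few patients unequal, at worst 33 v 27 with blocks of 4 and 6. Two levels control the split between shorter and longer strictures but not differences in length within a level. For patients already randomised, stratification cannot be added, and only adjustment for length remains.

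### Healthy, available donor tissue is an eligibility condition for the buccal graft but, lichen sclerosis apart, not for the penile skin graft, although every patient may be randomised to either

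*Protocol*

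**What the plan says.** Under Patients and Methods, "Patients will be randomly allocated into one of 2 groups", PSG or BMG, with 60 patients planned (30 per arm), open-label, in blocks of 2.

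Study Population has one inclusion criterion, an anterior stricture longer than 2 cm, and four exclusions. Three bear on tissue quality:

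- "Unhealthy/unavailable buccal mucosa", which is the BMG donor site;
- lichen sclerosis, which affects penile skin;
- "A scarred and unsalvageable urethral plate or scarred perineum", which concerns the urethra and perineum and not the shaft skin.

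The fourth concerns fistula, abscess and diverticulum.

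For the PSG arm, the surgical technique section describes "harvesting the graft from the lateral distal penile shaft in a transverse or longitudinal direction subcoronally". Pretreatment evaluation lists "Physical examination including BMI, oral, abdominal and penile examination and presence of supra-pubic catheter" and takes a history of earlier urethral procedures, but neither feeds an eligibility criterion on penile skin. The protocol does not say what happens if the allocated graft cannot be harvested.

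**The concern.** A randomised comparison of two grafts is clean only if each patient could receive either one when the allocation is made. The protocol applies this principle to one donor site and not to the other. A patient whose distal shaft skin is scarred, or was used in earlier surgery, passes every written criterion and may then be allocated an operation that cannot be done as described.

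Three things could follow:

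- **Switching.** The patient receives BMG although allocated PSG. Analysed as randomised, the contrast is diluted. Analysed as treated, the patient moves to the other arm, and the protection of randomisation is lost.
- **Dropping.** The patient leaves the PSG arm while similar patients stay in the BMG arm, so the arms differ in case mix.
- **Selective enrolment.** With no written rule, a clinician who can predict the next allocation may decline a patient with poor penile skin when PSG is due and enrol a similar patient when BMG is due.

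This matters for the trial's own rationale. The Introduction criticises earlier PSG and BMG comparisons for differences between the groups, and randomisation is meant to remove them.

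**Working it through.** **1. The eligibility list against the two operations (Protocol, Study Population and surgical technique).**

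| Requirement | BMG | PSG |
|---|---|---|
| Donor tissue healthy | Required | Lichen sclerosis excluded; nothing on scarring or other damage |
| Donor tissue available | Required | No criterion |
| Donor site examined beforehand | Yes (oral) | Yes (penile) |
| Examination tied to a donor-tissue criterion | Yes | Only for lichen sclerosis |

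The gap is therefore narrow: penile skin that is unhealthy for a reason other than lichen sclerosis, or is no longer available.

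**2. Predictability of allocation.** With 60 patients in blocks of 2 there are 60 / 2 = 30 blocks. In each block the second allocation is fixed by the first. If the enrolling staff know the block size, which the protocol states, and see earlier allocations, which is possible in an open-label trial, up to 30 of 60 allocations can be foreseen.

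**3. Size.** The only document figure available is 30 + 30 = 60, which is consistent. The protocol gives no significance level, power, effect size or frequency of unusable penile skin, so the consequence cannot be computed from it. What follows is illustration only. All inputs except n = 30 per arm are assumed.

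Let p be the share of PSG patients who cannot supply the graft, assumed to be 5%, 10% or 20%. The number affected is 30 × p. If all of them receive BMG, have BMG-like outcomes and are analysed as randomised, the difference shrinks by the factor 1 − p.

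For power, take a standardised difference d that gives 80% power at 30 per arm with two-sided alpha 0.05:

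d = (1.960 + 0.842) × √(2/30) = 0.723

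- Switched: power = Φ(d(1 − p) × √(30/2) − 1.960)
- Dropped from PSG only: power = Φ(d × √(30m/(30 + m)) − 1.960), with m = 30(1 − p)

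| p | PSG patients affected | Dilution factor | Power if switched | Power if dropped |
|---|---|---|---|---|
| 5% | 1.5 | 0.95 | 76% | 79% |
| 10% | 3 | 0.90 | 71% | 78% |
| 20% | 6 | 0.80 | 61% | 75% |

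Dropping costs little power. Its harm is selective loss, which the table does not measure.

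**4. The BMG side.** The Introduction states that BMG harvest is contraindicated in oral disease and in patients for whom general anaesthesia carries high risk, and it counts regional anaesthesia among the possible advantages of PSG. The exclusion list covers the mouth but not the anaesthetic risk. A patient at high anaesthetic risk is thus eligible and can be allocated BMG, against the protocol's own statement.

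**The case against.** The strongest reply is that the gap is small and partly covered. Lichen sclerosis is the one penile-skin condition that the protocol names as harming PSG results, and it is excluded. The fistula, urethral plate and perineum exclusions may remove some heavily operated patients. Earlier urethral procedures can be as minor as dilation, so recording them does not show that penile skin has been lost. Every patient has a penile examination, so a surgeon could see a deficiency in either arm. All of this stands and limits the likely number. It does not close the gap: none of these exclusions addresses scarred or used shaft skin, and an unwritten judgement is not reproducible and can depend on the next allocation.

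A reader might also infer three stronger claims that the document does not support:

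- **That long strictures will defeat PSG.** The Introduction says the opposite, listing suitability for longer grafts among the possible advantages of PSG. The technique section gives no maximum graft length.
- **That only the PSG arm can lose patients.** The anaesthesia contraindication opens a route on the BMG side as well.
- **That crossover or drop-out will occur.** This is a possible consequence of the written list. The protocol neither describes nor quantifies it.

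**Conclusion.** The asymmetry is real and can be read directly from the exclusion list. A patient with scarred or previously used penile skin can be randomised to a graft that cannot be harvested as described. Eligibility belongs in the protocol, so a separate analysis plan would not cure this.

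The consequence is possible and its size unknown. The 5-20% range, and the 1.5 to 6 PSG patients and power figures that follow from it, are assumptions without support in the document and show scale only. The net direction of any bias cannot be fixed either, because patients could be lost from both arms. The point is worth correcting because the change is specific and cheap.

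**What to change.** Extend the existing donor-tissue exclusion to penile skin, for example: *buccal mucosa or penile skin unhealthy or unavailable, as judged before randomisation*. Only patients judged suitable for both grafts would then be randomised. Make the judgement from the oral and penile examinations already listed, and record it for both sites on the screening form before allocation is revealed. No requirement on graft length is needed.

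Reconcile the exclusion list with the Introduction's statement on general anaesthesia and BMG harvest. Which way to resolve it is a clinical decision for the investigators.

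The cost is one line in the exclusion list and one entry on the screening form, with no new procedure. Recruitment may be slightly slower, and the result will apply to patients suitable for either graft.
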